NRT. In addition to the standard counseling described above, participants in the MTI arm will receive dual NRT (nicotine patch plus lozenge). An initial 2-week supply of 21 mg patches and 4 mg lozenges will be provided at the time of counseling or will be mailed to the participant within a week of randomization, and 3 additional 2-week supplies will be mailed out over the course of the subsequent 8 weeks. This mail-out model will allow us to assess participant use of the medications because participants will be contacted and asked how much NRT they used and if they would like to receive the next 2-week dose. Detailed information on each product, including instructions for use, will be provided in the take-home packet or emailed to the participant. We will inform patients about both single NRT use, as well as combined use, and participants will be given the opportunity to use the medications individually or together (participant choice, including none at all). Both patch and lozenge will be provided for four reasons. First, a number of studies demonstrate their efficacy when used singularly.⁵⁶ Second, they are both over the counter, increasing their utility within LCS settings where eligibility is minimal and instructions on use require nominal discussion. Third, whereas the patch provides a steady dose of nicotine throughout the day, the lozenge is used ad libitum and provides acute nicotine administration. These two mechanisms might appeal to smokers differently. Fourth, the majority of studies⁵⁷⁻⁶⁰ have shown that combined use of patch + lozenge is superior over placebo and single NRT products. Finally, the National Comprehensive Cancer Network Smoking Cessation Guidelines list combination NRT as first line pharmacotherapy. Those in the SC condition will receive standard counseling but no medications, and we will contact them every 2 weeks to inquire about use of any pharmacotherapies that they purchased on their own. At the time of patient contact regarding medications, research assistants will also assess point prevalence abstinence.

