These two week check-ins will occur either by phone or through MUSC REDCap's automated survey feature. Surveys can be automatically sent to patients for each two-week follow-up and patients can fill out the questions to indicate whether they would like more medications to be mailed to them. After the completion of the two-week check-ins, patients will be sent an Amazon gift code as a form of compensation. The payment will be as follows: \$10 for each completed two-week check-in and \$25 at the completion of the 3-month visit. If a participant completes at least 3 of the 4 check-ins, a \$30 bonus amazon gift code will be provided.

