
Follow-up: Participants will complete either online or paper assessments (no return clinic visit) at the end of treatment and 3 month follow-up session. Point prevalence abstinence will be established. At the 3-month follow-up all of the participants will also complete a biochemical verification of abstinence (see Outcome Definition below). Participants will be paid \$25 in the form of Amazon gift card codes for completion of the 3 month follow-up interview.

Assessments (Items with an asterisk will be tested as a mediator or moderator):

Demographic, Smoking History, and Current Medications Questionnaire: This questionnaire will obtain: 1) basic demographic information and 2) basic smoking status and history.^{12,15,62}

Tobacco Use Calendar (Timeline Followback): This standardized, validated, and reliable experimenter-administered rating scale⁶³⁻⁶⁵ will be used to obtain quantity and frequency estimates of cigarette consumption for a 30-day period prior to treatment and to retrospectively record daily use at each participant contact point.

***Fagerström Test for Nicotine Dependence (FTND) and Heaviness of Smoking Index (HSI):** The FTND is a commonly used scale for the measurement of severity of dependence on nicotine.⁴⁸ The HSI assesses 2 items from the FTND regarding amount smoked and time-to-first-cigarette.⁴⁹ The HSI has been shown to predict both behavioral and biochemical indices of smoking.⁴⁸⁻⁵⁰ In line with findings from our previous research^{42,43} and from other groups,^{66,67} we plan to test both the FTND and HSI as moderators of treatment.

***Medication Adherence Questionnaire (MAQ):** The MAQ is a self-report instrument composed of four items that assess participants’ history of medication adherence,^{68,69} which may moderate treatment outcomes.⁷⁰ Using the MAQ score, medication adherence will be assessed as a baseline moderator of treatment outcome.

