***Use of Pharmacotherapies:** We will determine the amount and frequency of NRT used (per product), and will also determine use of products we provide vs. purchase of additional products. For all participants, at each refill or contact point during the 8-week time frame, we will ask how many total patches and lozenges were used since the last contact, and how many were used each day. I will also incorporate a text-message based medication use assessment, as previously described. This novel approach will allow us to collect a daily medication diary from each participant, instead of relying on retrospective report. After calculating a percentage of medications taken, medication adherence will be assessed as a mediator of treatment outcomes.^{70,71}

Attitudes Towards NRT: Attitudes towards NRT may differ depending on the amount of NRT they elect to receive, the types of NRT selected, and the patient experience with the medication. We will assess 1) positive, and 2) negative attitudes towards NRT, as well as 3) general knowledge of NRT.^{32,72-76}

Motivation and Confidence to Quit: We will assess motivation and confidence to quit smoking using our modification of the Contemplation Ladder^{77,78} which assesses readiness to quit in the next month.

*Findings from screening: Lung screening findings will be defined as pulmonary findings (nodule, cancer, emphysema, enlarged lymph nodes) and coronary findings (calcification).

Adverse Events: We will assess adverse events at each NRT refill time point for the MTI group. For the SC group, we will ask about adverse events at each contact point after LCS. We will grade and report the severity of adverse events as described in Protection of Human Subjects. Participants who have significant side effects from NRT use will be encouraged to discontinue NRT use immediately.

Texting Satisfaction Survey: We will assess participant satisfaction with the texting intervention, including frequency, timing, and content of the text messages.

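### The two arms have differently worded rules for when adverse events are asked about; no 3-month question is scheduled for MTI, and for standard care it depends on an undefined term

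*Combined protocol and SAP*

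**What the plan says.** Section C2, Assessments, Adverse Events paragraph, has two adjacent sentences. For MTI: "We will assess adverse events at each NRT refill time point for the MTI group". For SC: "For the SC group, we will ask about adverse events at each contact point after LCS".

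The contacts these rules could attach to are described elsewhere in C2:

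- **Refills (NRT paragraph).** MTI receives a first 2-week supply, and "3 additional 2-week supplies will be mailed out over the course of the subsequent 8 weeks". Participants are asked whether they want the next supply, and they may choose to use none of the products.
- **SC contacts (NRT paragraph).** SC receives no study medication, but "we will contact them every 2 weeks to inquire about use of any pharmacotherapies that they purchased on their own".
- **Two-week check-ins (same part of C2).** These are done by phone or by automated REDCap survey. The surveys are "sent to patients for each two-week follow-up and patients can fill out the questions to indicate whether they would like more medications". The bonus rule fixes their number: "If a participant completes at least 3 of the 4 check-ins".
- **Later assessments (Follow-up paragraph).** Both arms are assessed at end of treatment and at 3 months.

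The wording of two neighbouring items bears on the meaning of a contact point. Use of Pharmacotherapies says "For all participants, at each refill or contact point during the 8-week time frame". The Tobacco Use Calendar says "retrospectively record daily use at each participant contact point", with no time limit.

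**The concern.** Adverse events that are asked about are recorded more completely than those left to be volunteered. If one arm is asked on more occasions or over a longer period, its recorded count rises for reasons unrelated to treatment. Here the rule that may be narrower applies to the arm given NRT, so any bias would tend to make MTI look safer than it is.

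Two features of the MTI rule add to this. First, it depends on a refill, and the text does not say whether the question is still put when a refill is declined. Participants who stop NRT because of side effects could plausibly be among those who decline, although the plan gives no data on this. Second, it ends with the supplies. The Data and Safety Monitoring Plan counts hospitalization and new cancer as serious, and in a lung-screening population either could occur between week 8 and month 3.

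**Working it through.** The plan states no figure to reproduce. The check is to set the passages side by side and see what each reading implies.

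**1. How far the MTI rule reaches.** Inputs from the NRT paragraph: 1 initial supply, 3 further supplies, 2 weeks each. Total supply is (1 + 3) × 2 = 8 weeks. If each new supply goes out as the last one ends, refills fall at about weeks 2, 4 and 6; those weeks are inferred, not stated. A wider reading counts every check-in as a refill time point, since the two-week survey carries the refill question. That gives four occasions. Neither reading reaches 3 months.

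**2. Whether other text supplies a 3-month question for MTI.** It does not.

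- *Sources of Materials* describes the questionnaires at intake, 8 weeks and 3 months as covering background, behavior and cognitions. Adverse events are not named.
- *Follow-up* and *Outcome Definition* cover smoking status and breath CO.
- *Protection Against Risk* covers the response once an effect is reported.
- *Data and Safety Monitoring Plan* covers staff training, grading and reporting, not when to ask.

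**3. How far the SC rule reaches.** Two readings are open.

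- *Broad.* The adverse-event sentence has no end date, and the Tobacco Use Calendar uses the same term without one. The 3-month follow-up is then included.
- *Narrow.* The routine SC contact is two-weekly, and the pharmacotherapy item pairs refill with contact point inside the 8-week period. The 3-month follow-up is then excluded.

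**4. The combinations.**

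| Reading of contact point | SC asked at 3 months | MTI asked at 3 months | During treatment |
|---|---|---|---|
| Broad | Yes, by inference | No | Equal or nearly equal across the two-week check-ins |
| Narrow | No | No | Equal or nearly equal |

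In the last column, *equal* applies if every check-in is a refill time point (4 and 4). *Nearly equal* applies if only actual refills count (MTI 3, SC 4).

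**5. Why no overall count or percentage is given.** The Text Messaging paragraph lists the check-ins, the end of treatment and the 3-month follow-up as separate items, and the Follow-up paragraph treats end of treatment as an assessment of its own. Nothing says whether the fourth check-in is that assessment. On the broad reading SC therefore has 4 + 1 = 5 scheduled questions if they coincide, or 4 + 1 + 1 = 6 if they do not. MTI has 3 or 4 depending on what a refill time point is. Any single ratio would rest on choices the plan does not make.

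**The case against.** The strongest reply is that the two sentences describe one schedule in two vocabularies. SC has no refills, so another term was needed for the same two-week contact. The NRT paragraph sets the two contacts in parallel, and the pharmacotherapy item joins the terms within 8 weeks. On this view the arms already match, and asking about adverse events after treatment ends is a matter of preference in a study described as minimal risk using over-the-counter products.

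Much of this stands. A reader might infer that the plan deliberately schedules a 3-month question for SC and withholds it from MTI. The documents do not support that: no passage names 3 months for adverse events in either arm, and the questionnaire description in Sources of Materials, which omits adverse events, does not separate the arms. It therefore counts against a 3-month question for SC as much as for MTI.

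The reply does not settle the matter. The adverse-event sentence lacks the 8-week limit that the pharmacotherapy item carries, so staff following the text could reasonably ask SC at 3 months and not MTI. The parallel reading also leaves open what happens when a refill is declined.

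On consequence, the Statistical Analysis paragraph plans no comparison of adverse events by arm, and the semiannual safety report is of aggregate data. Staff are trained to identify events, serious-event reporting has no week-8 cut-off, and the planned 3-month CO sample involves live contact with staff. These reduce the harm, though none is a scheduled question.

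**Conclusion.** The point holds as a minor one. The rules for asking about adverse events are worded differently by arm and turn on an undefined term. MTI has no scheduled 3-month question on any reading. SC has one only if contact point is read broadly. Either the arms differ at 3 months or neither is asked.

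A by-arm tabulation could under-count MTI, but the size of that effect cannot be estimated, since the plan gives no event rate. A reader might also infer a definite percentage shortfall in scheduled questions, or a biased safety conclusion. Neither is supported: the number of contacts is not fixed by the text, and no by-arm safety conclusion is planned. The abstinence outcomes are unaffected.

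The conclusion assumes that the survey and phone scripts, which are not part of the documents, follow the protocol wording.

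**What to change.** Replace the two sentences with a single rule for both arms: *The same AE question is asked in both arms at every two-week check-in, at the end-of-treatment assessment and at the 3-month follow-up, whether or not a refill is requested.* This wording works whether or not the fourth check-in doubles as the end-of-treatment assessment, and it removes the need to define a contact point for this purpose.

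Add the item to the phone script and to the REDCap check-in, end-of-treatment and 3-month surveys. The surveys matter because an automated check-in may involve no conversation in which an event could be volunteered.

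The cost is one sentence and one survey item at contacts that already occur, with no extra visits. The downside is slightly longer contacts.

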Outcome Definition: For our primary outcome, consistent with [name] past quitline clinical trials,^{13,15,62} abstinence will be defined as self-reported 7-day point prevalence abstinence. We will ask participants during follow-up, "Have you smoked a cigarette, even a puff, in the past 7 days?" An answer of "no" to this item will be considered abstinence. We will also ask about number of days since the participant quit, to retrospectively compute longer-term quit rates, including 30-day point prevalence abstinence. At the end of treatment and the 3-month follow-up, we will also attempt to obtain smoking status via text. The text to participants will be the same point prevalence question described above. After comparing these data to the interview-based data, we will be able to determine if texting is a viable method for collecting smoking cessation data in a larger trial. I will also attempt to obtain biochemical verification at baseline and the 3-month follow-up using breath carbon monoxide (CO). Biochemical verification is often used in smoking cessation studies to objectively confirm self-reported smoking status.⁷⁹ If the baseline visit occurs in person, we will obtain breath CO at the visit. If the baseline visit occurs remotely, then a breath CO monitor will be mailed to the participant. At the 3-month visit, we will mail a breath CO monitor to participants who did not receive one at baseline (i.e., those who completed the baseline visit in person). Breath CO monitors will be mailed with instructions for use. At a prearranged time, participants will be sent a doxy.me link. Doxy.me is a secure, virtual telemedicine "room." Participants will virtually meet with research staff and will complete the breath CO sample live so that we can be sure it was the participant who provided the sample and reduce the chance of sample falsification. The CO device will also email a report of the CO sample to research staff. Studies examining the validity of smokers' self-reports have noted that differences between self-report and biochemical validation have been relatively small in absolute terms, so we will use self-report for primary abstinence outcomes and CO for secondary analyses of outcomes.^{81,82}

C3. Statistical Considerations

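### For participants with an in-person baseline, the 3-month breath CO sample may fall after the 7-day self-report it is meant to check, because the monitor is mailed only at that visit and no maximum gap is set

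*Combined protocol and SAP*

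**What the plan says.** All of this is in section C2 of the combined protocol and SAP unless stated otherwise.

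- **Self-report.** Under Outcome Definition, "abstinence will be defined as self-reported 7-day point prevalence abstinence". The item is "Have you smoked a cigarette, even a puff, in the past 7 days", so it describes the week before it is answered.
- **How the 3-month answer is collected.** Under Follow-up: "Participants will complete either online or paper assessments (no return clinic visit) at the end of treatment and 3 month follow-up session". Other places point to an interview. The payment sentence under Follow-up calls the 3-month contact an interview, Outcome Definition refers to interview-based data, and Sources of Materials (Protection of Human Subjects) describes the questionnaires as administered by an interviewer.
- **CO at 3 months.** Under Follow-up: "At the 3-month follow-up all of the participants will also complete a biochemical verification of abstinence". Outcome Definition is softer and says only that verification will be attempted.
- **Who has a monitor, and when.** "If the baseline visit occurs remotely, then a breath CO monitor will be mailed to the participant". For the rest, "At the 3-month visit, we will mail a breath CO monitor to participants who did not receive one at baseline"; the text explains that these are the people whose baseline was in person.
- **When the sample is given.** "At a prearranged time, participants will be sent a doxy.me link", and the sample is given live with research staff watching.
- **Role of CO.** Published comparisons found small differences between self-report and biochemical tests, "so we will use self-report for primary abstinence outcomes and CO for secondary analyses of outcomes".

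**The concern.** A breath sample can check a statement about the past week only if both refer to the same period, or if the statement is renewed when the sample is taken. The plan describes two sequences, set by where the baseline took place. In one, the monitor is already in the home at 3 months. In the other, it is posted only at that point, and the sample waits for delivery and a scheduled call.

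If the answer on the form comes first and is not repeated, a discordant pair has two explanations. The person may have misreported, or may have truthfully reported abstinence and then smoked. A concordant pair is also less secure, because someone who reported abstinence falsely could stop once the monitor arrives.

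CO is the only biochemical measure, and 3 months is its only time point after treatment. Secondary Aim 2 is the 3-month effect size, and section C3 says the pilot's estimates are meant to power a later trial. An ambiguous CO-verified rate would carry into that use.

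**Working it through.** **1. The plan's own precision figures.** Section C3 specifies exact 95% intervals with 40 per arm. The Clopper-Pearson limits are the 0.025 quantile of Beta(x, n−x+1) and the 0.975 quantile of Beta(x+1, n−x).

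| x/n | Computed interval | Half width | Table 2 |
|---|---|---|---|
| 20/40 | 0.338 to 0.662 | 0.162 | (0.34, 0.66), 0.16 |
| 12/40 | 0.166 to 0.465 | 0.150 | (0.17, 0.47), 0.15 |
| 4/40 | 0.028 to 0.237 | 0.104 | (0.03, 0.24), 0.10 |

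Table 2 reproduces, and the timing question does not alter it.

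**2. The order of events.** For an in-person baseline the stated steps are: 3-month visit, monitor mailed at that visit, delivery, prearranged call, sample. The gap between an answer given at the visit and the sample is then at least the mailing time. For a remote baseline the mailing step is absent. The consent section makes Lancaster, Chester, Florence and Columbia remote only, which is four of the eight sites listed in C4, and Charleston also offers remote baselines. The in-person share is not given.

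**3. How much lag matters.** Let L be the days from answer to sample and W the days of smoking that a breath CO reading reflects. The documents give neither; W is assumed to be 0.5, 1 or 2 days. The overlap between the CO period and the reported week is max(0, min(0, L) − max(−7, L−W)).

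| L (days) | W = 0.5 | W = 1 | W = 2 |
|---|---|---|---|
| 0 | 0.5 | 1 | 2 |
| 1 | 0 | 0 | 1 |
| 2 or more | 0 | 0 | 0 |

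Under these assumptions a lag of two days removes all overlap. If the question is asked again on the call, the CO period lies inside the new 7-day window at any L. That new window shares max(0, 7−L) days with the first: 4 days at L = 3, none at L = 7 or more.

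**4. Size of the effect on a CO-verified rate.** Let m be the truthful abstainers per arm, r the weekly relapse probability and w the lag in weeks. Expected relapses before the sample are m × (1 − (1−r)^w). Assumptions: r from 0.01 to 0.05, w from 1 to 3, every baseline in person, and every relapse detected by CO and counted as not verified. The documents give no CO cut-off or discordance rule.

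- Rate 0.30, m = 12. Low: 12 × 0.01 = 0.12 people; 0.12/40 = 0.3 points. High: 12 × (1 − 0.95³) = 12 × 0.1426 = 1.71 people; 1.71/40 = 4.3 points.
- Rate 0.10, m = 4. Low: 4 × 0.01 = 0.04 people; 0.1 points. High: 4 × 0.1426 = 0.57 people; 1.4 points.

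The loss scales with the in-person share: at an assumed one half, the 4.3 points become about 2.1. False confirmations raise the CO-verified rate and so offset part of the loss. With true rates of 0.30 and 0.10 in the two arms, the high case would narrow the difference by 4.3 − 1.4 = 2.9 points if all baselines were in person.

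**The case against.** The best defence is that the mailing phrase is loose. The plan uses the word visit for remote sessions too, and there is no return to the clinic. The video call with staff may therefore itself be the 3-month visit, with the monitor sent for that time point. The interview wording supports this: staff may put the 7-day question live, perhaps on the same call. This reading is possible, but no passage states it, and the literal sequence conflicts with it. The plan should say which is meant.

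Several stronger inferences are tempting and not supported:

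- *That CO and self-report always cover different days, for everyone.* The mailing sentence excludes remote-baseline participants, and no passage dates the answer relative to the call.
- *That CO cannot verify self-report.* Staff are on the call and could ask. The Timeline Followback records daily use at each contact, and participants are asked how long ago they quit. Either could bridge a gap, although the plan does not use them to define CO-verified abstinence.
- *That the plan relies on agreement with its own CO data to justify self-report as primary.* It relies on published studies.
- *That the treatment comparison is biased through allocation.* The lag depends on baseline mode, not on assigned arm. Any narrowing of the difference arises because the loss is proportional to the number of abstainers.

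It is also fair that the effect is small beside the sampling error: at a rate of 0.30, even 4.3 points compares with a half width of 15 points.

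**Conclusion.** The concern holds in a limited form. For participants with an in-person baseline, the text followed literally places the breath sample after the 7-day answer, and nothing in the plan limits the gap or renews the question. Self-report/CO discordance at 3 months could then not be read cleanly as misreporting.

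The size is uncertain because it depends on the lag, the relapse rate and the in-person share, none of which the documents give. Under the stated assumptions, and before any offset, the loss ranges from 0.3 to 4.3 points at a rate of 0.30 and from 0.1 to 1.4 points at 0.10. These are ceilings with respect to the in-person share.

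The consequence is confined to a secondary analysis at one time point. The primary Week 8 self-report outcome is untouched. The point still merits a change, because the error would be systematic and is avoidable on a call that is already planned.

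**What to change.** Revise Outcome Definition in section C2 as follows:

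1. Mail monitors to participants with an in-person baseline far enough ahead to arrive before the 3-month date, and book the CO call for that date.
2. Have staff ask the same 7-day question on the call, immediately before the breath sample.
3. Define CO-verified 3-month abstinence from that same-call pair. State the CO cut-off and how discordant or missing CO results are handled.
4. Keep the existing self-report outcome as it is.
5. Record the dates of the self-report and of the CO sample, and report the interval and the agreement by baseline mode.

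The cost is protocol wording, earlier posting and one added question. The downside is that some monitors will go to people who are later lost to follow-up.

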prospect theory suggest that decision makers cognitively organize information relevant to decisions in terms of potential gains (i.e., benefits) or potential losses (i.e., costs). Several previous studies have shown that gain-framed messages are more effective than loss-framed messages for increasing intentions to quit, quit attempts, and smoking cessation in general populations of smokers.^{15,37-41} I plan to use text messaging, a novel approach in the context of lung screening, to deliver gain-framed texts regarding smoking cessation to patients after their scan. Further, texting will allow me to deliver other types of messaging, such as medication reminders and medication adherence assessments. The use of messaging and framing to increase medication adherence is also a novel difference from the currently funded LCS R01 and past clinical trials on message framing. Integrating medication reminders with a text intervention may promote medication adherence, which, coupled with the effects of gain-framed messaging, could further promote abstinence. The text messages will be delivered through a system already in place at Hollings Cancer Center (HCC). Thus, this text protocol could be easily implemented as standard care at the HCC LCS Program, and this type of dissemination and implementation work could be the topic of future research endeavors. Further, the potential exists for the programmable texts to be easily disseminated to other sites.

A4. Summary of Primary and Secondary Aims. In the proposed study, I will investigate 2 complementary treatments: NRT and gain-framed text messaging designed for LCS patients. The primary aim is to determine an effect size estimate for the intervention at the end of treatment. I will also examine abstinence rates among the two treatment arms. I hypothesize that an NRT intervention plus gain-framed text messaging will produce higher rates of smoking cessation at the end of treatment compared to standard care for LCS patients. As a secondary aim, I plan to develop effect size estimates for rates of smoking cessation at the 3-month follow-up.

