See letter of support from consultant, [name], Director of the HCC Biostatistics Shared Resource. Sample size justification: Eighty participants (40 per group) will be enrolled. A sample size of 40 will allow us to establish estimates of abstinence with 95% confidence intervals (CI) for each arm, and to assess the precision in our estimates. The goal is to establish reasonably precise effect sizes to power a future study so we do not expect to achieve statistical significance in group comparisons. 95% CI and corresponding half widths for exemplar abstinence rates are provided in Table 2. With 40 patients per arm and an observed abstinence rate of 0.30, we can be 95% confident that the true abstinence rate is between 0.17 and 0.47 for that intervention.

Statistical Analysis: Aims 1 and 2 will be achieved by estimating abstinence rates with exact 95% CIs. Differences in rates and the 95% CIs for the differences will also be estimated. Baseline clinical and demographic variables will be assessed with summary statistics and reported by group, and compared to evaluate balance across groups. While the main aim of this pilot trial is to establish effect size estimates, we will also conduct a preliminary examination of between group differences in abstinence using logistic regression. With respect to exploratory analyses, logistic regression will also be implemented to evaluate effects of mediators and moderators of treatment on abstinence, and linear regression will be used to compare costs in the two arms. Given the pilot nature of this study, emphasis is on estimating effect sizes and variances and not statistical significance of associations. A sample size of 40 patients per group should provide sufficient preliminary data to guide me in my future research in this area.

Table 2. Example Effect Size Estimates

Observed Rate of Abstinence	95% CI	Half Width
0.50	(0.34,0.66)	0.16
0.30	(0.17,0.47)	0.15
0.10	(0.03,0.24)	0.10

C4. Recruitment, Feasibility, and Timeline

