Patients eligible for this study will come from the LCS programs at HCC Downtown, Mount Pleasant, North Charleston, West Ashley, Lancaster, Chester, Florence, and Columbia. [name] is the Co-Director of program, and I will have full access to all LCS patients who smoke. To date, the program has screened more than 300 patients and is expanding outreach efforts. Between 11/1/16 and 2/1/17, 21 current smokers were screened (7 per month). Not all patients may be interested in participating in a research study, so I conservatively estimate that I could recruit 2 current smokers per month. The LCS program is in the midst of launching a \$30,000 ad campaign, and the nurse practitioner dedicated to the program is visiting primary care practices every week. Thus, due to these ongoing outreach activities, the program projects screening at least 20 current smokers per month over the next 6 months, and I do not anticipate a problem with recruitment. The study timeline is presented in Table 3.

Table 3. Study Timeline

Months 1-12:	IRB approval, create texting materials
Months 13-17:	Test the text protocol; obtain medication, train staff
Months 18-49:	Recruit 80 participants and follow for 3 months
Months 50-60:	Follow-up, data analyses, prepare presentations and publications.

D. Summary and Future Directions

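### Does the sample-size justification fail because Table 2 shows per-arm precision and not the precision of the between-arm difference?

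*Combined protocol and SAP*

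**What the plan says.** Section A4 of the combined protocol and SAP states: "The primary aim is to determine an effect size estimate for the intervention at the end of treatment". Aim 1 in the Specific Aims has two parts: to evaluate abstinence rates, and to derive effect sizes for standard against enhanced treatment.

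Section C3 sets the sample size: "Eighty participants (40 per group) will be enrolled". It explains that 40 per arm yields a 95% interval for the abstinence rate in each arm, and adds that significant group comparisons are not expected. The purpose it gives is this: "The goal is to establish reasonably precise effect sizes to power a future study". The supporting figures stand under "Table 2. Example Effect Size Estimates", where the first column is the observed abstinence rate (0.50, 0.30, 0.10) and the others are its 95% interval and half-width.

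The analysis paragraph of C3 uses exact intervals for the rates and continues: "Differences in rates and the 95% CIs for the differences will also be estimated". It names no method for that second interval and no expected width.

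On accrual, section C4 reports 21 current smokers screened in three months, 7 per month, and says "I conservatively estimate that I could recruit 2 current smokers per month". It then describes an advertising campaign and outreach, after which "the program projects screening at least 20 current smokers per month over the next 6 months". Table 3 gives Months 18-49 to recruiting 80 "participants and follow for 3 months", and Months 50-60 also list follow-up.

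**The concern.** The quantity the pilot exists to estimate and the quantity whose precision is displayed are not the same. A difference between two independent rates has a larger variance than either rate. A reader who trusts the table's title could carry 0.10 to 0.16 forward as the precision of the treatment effect.

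What would be at stake is the next trial. As an illustration, assume a control rate of 0.10, two-sided 5% significance, 80% power and the unpooled formula. An observed difference of 0.20 then implies about 59 per arm. The ends of that difference's own 95% interval, 0.023 and 0.366, imply about 2,900 and 20 per arm. Nothing in Table 2 shows a spread of that kind.

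The accrual figures seem to add to this. The only enrolment rate in C4, multiplied by the length of the recruitment window, falls short of 80, and fewer participants would widen every interval.

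**Working it through.** **Inputs.** 40 per arm, 95% two-sided, and exemplar rates 0.50, 0.30 and 0.10 (C3 and Table 2); exact intervals for single rates (C3); 7 and 20 screened per month, 2 enrolled per month (C4); Months 18-49 (Table 3). The plan gives no method for the difference. I use Newcombe's interval, built from Wilson limits, with the uncorrected Wald interval as a check.

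**Step 1: reproduce Table 2.** Clopper-Pearson limits for x of n = 40 are the 0.025 quantile of Beta(x, n-x+1) and the 0.975 quantile of Beta(x+1, n-x).

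- 20/40: 0.338 to 0.662, half-width 0.162
- 12/40: 0.166 to 0.465, half-width 0.150
- 4/40: 0.028 to 0.237, half-width 0.104

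All three rows agree with the plan after rounding. There is no arithmetic error.

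**Step 2: interval for the difference.** With d = p1 - p2 and Wilson limits (l, u) for each arm:

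- lower = d - √[(p1 - l1)² + (u2 - p2)²]
- upper = d + √[(u1 - p1)² + (p2 - l2)²]

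For 0.30 v 0.10 the Wilson limits are 0.1807 to 0.4543 and 0.0396 to 0.2305.

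- lower = 0.20 - √(0.1193² + 0.1305²) = 0.20 - 0.177 = 0.023
- upper = 0.20 + √(0.1543² + 0.0604²) = 0.20 + 0.166 = 0.366
- half-width = (0.366 - 0.023)/2 = 0.171

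Wald check: 1.96 × √(0.30×0.70/40 + 0.10×0.90/40) = 1.96 × √0.0075 = 0.170.

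| Rates | Newcombe 95% interval | Newcombe half-width | Wald half-width |
|---|---|---|---|
| 0.50 v 0.50 | -0.209 to 0.209 | 0.209 | 0.219 |
| 0.50 v 0.30 | -0.014 to 0.390 | 0.202 | 0.210 |
| 0.30 v 0.30 | -0.195 to 0.195 | 0.195 | 0.201 |
| 0.50 v 0.10 | 0.203 to 0.560 | 0.179 | 0.181 |
| 0.30 v 0.10 | 0.023 to 0.366 | 0.171 | 0.170 |
| 0.10 v 0.10 | -0.144 to 0.144 | 0.144 | 0.131 |

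The two methods differ by at most about 0.012, so leaving the method unnamed matters little. A continuity correction would add 1/40 = 0.025 to each Wald figure.

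**Step 3: is the extra width peculiar to this plan?** No. With equal rates and equal arms, the Wald half-width for a difference is √2 = 1.41 times the single-arm Wald half-width, in any two-arm trial. A ratio of the Newcombe figures to Table 2's exact half-widths would mix two methods, so I do not rely on one.

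**Step 4: accrual.** The window is 49 - 18 + 1 = 32 months.

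- At 2 per month: 2 × 32 = 64.
- Needed for 80: 80/32 = 2.5 per month.
- Share implied by 2 enrolled of 7 screened: 2/7 = 28.6%. The same share of 20 screened is 5.7 per month, and 80/5.7 is about 14 months.
- At that share, 2.5 per month needs 2.5/(2/7) = 8.75 screened per month.
- If the three-month follow-up must also fit inside the window, 29 months remain: 80/29 = 2.76 per month, or 2.76/(2/7) = 9.7 screened per month.

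The target therefore needs screening volume to rise from 7 to between 9 and 10 per month, under half of the projected 20.

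**Step 5: if only 64 were enrolled.** With 32 per arm, Wald half-widths grow by √(40/32) = 1.118, from 0.131-0.219 to 0.147-0.245.

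**The case for a change.** The best case for a change is that the plan chose precision, not power, as its justification, and so owes the reader the precision of the quantity named as its primary aim. Saying that an interval will be computed is not the same as saying how wide it will be. The table's title points to the wrong quantity, and the remedy would cost a new title and a few rows.

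Part of this stands. The title is loose, the expected width of the difference appears nowhere, and its method is unnamed. It is also true that the projection of 20 screened per month covers only six months and is never turned into an enrolment rate.

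The rest does not carry. Only the title could mislead: the column heading, the sentence introducing the table and the worked example at 0.30 all speak of an abstinence rate in one arm. Per-arm rates are part of Aim 1, so Table 2 is not beside the point. The statement that significance is not expected already warns that the contrast will be imprecise. Nothing in the plan says that the later trial will be sized on the observed difference alone, so a disclaimer would answer a claim the plan does not make. The figure of 64 applies the rate given alongside 7 screened per month to a period for which the plan expects more.

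**Conclusion.** No change is needed. The narrow observation is correct: at 40 per arm the 95% interval for the difference has a half-width of about 0.17 to 0.21 by Newcombe, or 0.14 if both rates are 0.10 (Wald 0.13 to 0.22 over all pairs), and the plan does not say so. It is a missing illustration with a loosely worded title, and filling it brings no gain. The analysis already includes the difference with its 95% interval, any standard method gives nearly the same width, and whoever sizes the later trial will have that interval in hand. Retitling the table or adding rows would alter no estimate, analysis, decision rule or incorrect figure. The enrolment point does not change this, since 80 is reachable with screening well below the projected volume.

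The half-widths assume 40 analysed per arm, rates within Table 2's range and no continuity correction. C3 gives no allowance for dropout, so losses would widen the intervals, by about 12% if 32 per arm were analysed. The accrual reading assumes that roughly the same share of screened smokers enrols and that screening volume does rise above 7 per month through the recruitment window.
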